1.2 Preclinical Data

Since its introduction in the 1970s, propofol has become the most widely used IV hypnotic in clinical use today. Building on work on the sedative properties of phenol derivatives in mice, propofol was developed in the United Kingdom by Imperial Chemical Industries as ICI 35868. The current formulation was launched in 1986¹⁴.

1.3 Clinical Data to Date

Propofol is used for induction and maintenance of anesthesia and for sedation in and outside the operating room. Its mechanism of action is likely the enhancement of γ -aminobutyric acid (GABA)-induced chloride currents. Propofol causes a dose-dependent decrease in arterial blood pressure through a decrease in cardiac output and systemic vascular resistance and produces moderate respiratory depression. A unique action of propofol is its antiemetic effect, even at concentrations less than those producing sedation¹⁴.

1.4 Dose Rationale and Risk/Benefits

Propofol is suitable for the induction and maintenance of anesthesia.

The IV induction dose is 1 to 2.5 mg/kg.

Maintenance dose is 50-150 μ g/kg/min IV combined with N₂O or an opiate. The infusion rate is titrated to individual requirements and the surgical stimulus¹⁴.

Induction of anesthesia with propofol is often associated with pain on injection, apnea, hypotension, and, rarely, thrombophlebitis of the vein into which propofol is injected¹⁴.

2 Study Objectives

The objective of this study is to evaluate the effects of TIVA versus IA on intraoperative visual field in ESS for the treatment of advanced paranasal sinus disease.

SPECIFIC AIMS

1. Determine the effect of total intravenous versus inhaled anesthesia on intraoperative visual field in endoscopic sinus surgery for advanced paranasal sinus disease

This study seeks to evaluate the effect of total intravenous anesthesia (TIVA) on the intraoperative visual field during endoscopic sinus surgery (ESS). Subgroup analysis of patients with allergic fungal sinusitis, pan-sinus opacification and nasal polyposis will further evaluate the role of TIVA in advanced sinus disease.

CONFIDENTIAL

This material is the property of Ochsner Clinic Foundation. Do not disclose or use except as authorized in writing by the study sponsor

2. Evaluate clinical outcomes associated with choice of total intravenous versus inhaled anesthesia in endoscopic sinus surgery

Clinical outcomes among patients receiving TIVA versus IA will be made with assessment of change in quality of life scores, pharmacologic effects (postoperative nausea and vomiting, recovery time) and surgical complications.

3. Evaluate relative costs associated with total intravenous versus inhaled anesthesia in endoscopic sinus surgery

Comparative cost analysis will be included to evaluate potential barriers to implementation of total intravenous anesthesia in endoscopic sinus surgery.

3 Study Design

3.1 General Design

Double blind, randomized controlled trial of total intravenous versus inhaled anesthetic for maintenance of anesthesia during endoscopic sinus surgery.

3.2 Primary Study Endpoints

110 patients will be enrolled for study participation. Validated measure of intraoperative visual field will be utilized for primary outcome measure.

3.3 Secondary Study Endpoints

Secondary outcome measures include change in sinus-related quality-of-life, intraoperative bleeding, surgical time, post anesthesia care unit recovery time, postoperative nausea and vomiting (PONV), complications and response duration.

3.4 Primary Safety Endpoints

Safety endpoints include adverse surgical (intraoperative orbital/dural injury and postoperative hemorrhage/cerebrospinal fluid leak) and pharmacologic (severe PONV) events.

4 Subject Selection and Withdrawal

4.1 Inclusion Criteria

Inclusion criteria include English-speaking patients undergoing endoscopic sinus surgery for the treatment of inflammatory paranasal sinus disease, including subgroups of patients with allergic fungal sinusitis, chronic rhinosinusitis with nasal polyposis, chronic rhinosinusitis with eosinophilia and rhinosinusitis with pan-sinus opacification.

4.2 Exclusion Criteria

Exclusion criteria includes noninflammatory sinonasal disease, disease extending through the skull base or orbital wall, patients <18 years old, American Society of Anesthesiologists Preoperative Health Status >II, known non-pharmacologic coagulopathy (platelet < 50000/mL, INR>1.2), preoperative anticoagulants within 7 days of surgery and allergy to one of the study medications.

4.3 Subject Recruitment and Screening

Patients will be screened for study inclusion by the principal investigator ([name]) during their preoperative visit in the Department of Otolaryngology. Those meeting inclusion criteria will be introduced to the study at this time. A full description of the research purpose, personnel, procedures, risks and benefits will be presented, and a copy of the study consent documentation will be provided for home review.

4.4 Early Withdrawal of Subjects

4.4.1 When and How to Withdraw Subjects

Study personnel will remain available to participants at all times during the study period, and may be reached via the hospital operator. Withdraw notification can be given at any time, and will be immediately reported to the clinical coordinator for documentation.

4.4.2 Data Collection and Follow-up for Withdrawn Subjects

Completion of study participation will have no bearing on clinical follow-up. Withdrawn subjects will complete follow-up as clinically indicated, without further data collection.

5 Study Drug

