8.1 Definitions

Adverse Event

An **adverse event** (AE) is any symptom, sign, illness or experience that develops or worsens in severity during the course of the study. Intercurrent illnesses or injuries should be regarded as adverse events. Abnormal results of diagnostic procedures are considered to be adverse events if the abnormality:

- results in study withdrawal
- is associated with a serious adverse event
- is associated with clinical signs or symptoms
- leads to additional treatment or to further diagnostic tests
- is considered by the investigator to be of clinical significance

Serious Adverse Event

Adverse events are classified as serious or non-serious. A **serious adverse event** is any AE that is:

- fatal
- life-threatening
- requires or prolongs hospital stay
- results in persistent or significant disability or incapacity

CONFIDENTIAL

This material is the property of Ochsner Clinic Foundation. Do not disclose or use except as authorized in writing by the study sponsor

- a congenital anomaly or birth defect
- an important medical event

Important medical events are those that may not be immediately life threatening, but are clearly of major clinical significance. They may jeopardize the subject, and may require intervention to prevent one of the other serious outcomes noted above. For example, drug overdose or abuse, a seizure that did not result in in-patient hospitalization, or intensive treatment of bronchospasm in an emergency department would typically be considered serious.

All adverse events that do not meet any of the criteria for serious should be regarded as ***non-serious adverse events***.

Adverse Event Reporting Period

The study period during which adverse events must be reported is normally defined as the period from the initiation of any study procedures to the end of the study treatment follow-up. For this study, the study treatment follow-up is defined as 30 days following surgery.

Hospitalization, Prolonged Hospitalization or Surgery

Any adverse event that results in hospitalization or prolonged hospitalization should be documented and reported as a serious adverse event unless specifically instructed otherwise in this protocol. Any condition responsible for surgery should be documented as an adverse event if the condition meets the criteria for an adverse event.

Neither the condition, hospitalization, prolonged hospitalization, nor surgery are reported as an adverse event in the following circumstances:

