8.2 Recording of Adverse Events

At each contact with the subject, the investigator must seek information on adverse events by specific questioning and, as appropriate, by examination.

All adverse events occurring during the study period must be recorded. The clinical course of each event should be followed until resolution, stabilization, or until it has been determined that the study treatment or participation is not the cause. Serious adverse events that are still ongoing at the end of the study period must be followed up to determine the final outcome. Any serious adverse event that occurs after the study period and is considered to be possibly related to the study treatment or study participation should be recorded and reported immediately.

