8.2.1 EC/IRB Notification by Investigator

Reports of all serious adverse events (including follow-up information) must be submitted to the EC/IRB within 10 working days. Copies of each report and documentation of EC/IRB notification and receipt will be kept in the Clinical Investigator's binder.

9 Data Handling and Record Keeping

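### Section 4.4.2 ends data collection at withdrawal with no safety exception, contradicting the section 8 duties to record, follow and report adverse events to 30 days after surgery

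*Combined protocol and SAP*

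**What the plan says.** Section 4.4.2 gives the rule for patients who leave the study: "Withdrawn subjects will complete follow-up as clinically indicated, without further data collection". Section 4.4.1 puts no limit on when this can happen: "Withdraw notification can be given at any time".

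Section 8 sets the safety duties:

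- **8.1, reporting period.** It opens with the first study procedure and closes at the end of follow-up, and "the study treatment follow-up is defined as 30 days following surgery".
- **8.2, ascertainment.** "At each contact with the subject, the investigator must seek information on adverse events by specific questioning".
- **8.2, recording.** "All adverse events occurring during the study period must be recorded".
- **8.2, follow-up.** "Serious adverse events that are still ongoing at the end of the study period must be followed up to determine the final outcome".
- **8.2, later events.** For serious events, the duty extends to any one which "occurs after the study period and is considered to be possibly related to the study treatment or study participation should be recorded and reported immediately", as the closing sentence puts it.
- **8.2.1, reporting.** "Reports of all serious adverse events (including follow-up information) must be submitted to the EC/IRB within 10 working days".

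Section 9.1 deals with a narrower group, patients who revoke authorization to use their health information. For them, staff should try to get permission to collect vital status as a minimum. Section 3.4 names postoperative hemorrhage and cerebrospinal fluid leak among the safety endpoints.

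**The concern.** Section 4.4.2 covers all data, and section 8 covers all subjects. They collide for a patient who withdraws between surgery and day 30. Followed literally, 4.4.2 would leave a later hemorrhage or CSF leak out of the study record, while section 8 would put it in.

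Two things are at stake. The first is whether the safety comparison between the two anesthetic arms includes every endpoint event. Patients may withdraw because of a complication, so any lost events need not be a random sample; this is plausible, but the documents do not show it. The second is whether a serious event in a withdrawn patient reaches the EC/IRB. As written, both depend on which section the staff member has in mind.

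**Working it through.** The plan states no figure on this point, so the check is a comparison of texts, followed by a timing check and a note on why no estimate is made.

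**1. One patient under each rule.** Suppose a patient withdraws on day 5 without revoking authorization and bleeds on day 10.

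| Question | Section 4.4.2 | Section 8 |
|---|---|---|
| Is day 10 inside the collection window? | No, collection ended on day 5 | Yes, 10 < 30 (8.1) |
| Is the bleed recorded? | No | Yes (8.2) |
| If serious and ongoing at day 30, is it followed? | No | Yes, to outcome (8.2) |
| If serious, is it reported to the EC/IRB? | No data from which to report | Yes (8.2.1) |

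**2. Could the study period end at withdrawal?** Section 8.1 ties the end of the period to surgery, not to withdrawal. Even if the period did stop on day 5, the last sentence of 8.2 would still require a possibly related serious event after it to be recorded and reported. Section 4.4.2 rules that out, so the conflict remains.

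**3. Could a withdrawn patient fall outside section 8 altogether?** No passage says so, and 4.4.2 itself still calls these people subjects. Section 8.1 also classes an abnormal diagnostic result as an adverse event when it leads to withdrawal. Section 8.2 wants each event followed until it settles or is judged unrelated to the study, but 4.4.2 stops collection at the moment this kind of event arises.

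**4. Does section 9.1 settle it?** It applies only when authorization is revoked. Taken with 4.4.2, the effect is odd: staff seek at least vital status from patients who revoke authorization, and nothing from patients who simply withdraw.

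**5. Timing of the routine visits.** The week 1 and week 4 evaluations appear both in the surgical protocol (5.2) and in section 6. Week 1 is 1 × 7 = day 7 and week 4 is 4 × 7 = day 28. Both are within 30 days, so chart information for the safety window should exist without any added visit.

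**6. Size.** The expected number of missed events is (withdrawals between surgery and day 30) × (risk of an event after withdrawal and by day 30). The documents give neither term. The dropout allowance in 7.1, 110 − 104 = 6 patients, cannot stand in for the first. It inflates a sample size for an outcome filmed before surgery ends, so it neither estimates nor caps withdrawals after surgery.

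**The case against.** The strongest reply is that 4.4.2 is the specific rule for withdrawn patients and section 8 the general rule for everyone else, so the specific rule governs. Ending research data collection at withdrawal while care continues is a recognisable design position. On this view the last sentence of 8.2 acts as a safety backstop for the events that matter most. The consent form, HIPAA authorization and monitoring plan (Attachments A, B and D) are also where use of data after withdrawal might be set out, and they were not available for this review.

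Some of this stands. The attachments may say more. The exposure is narrow: clinical care continues, events before withdrawal are already recordable, orbital or dural injury is counted intraoperatively, and there are no study-only visits whose burden would prompt patients to leave after surgery.

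The rest does not. No passage gives 4.4.2 precedence, and giving it precedence is exactly what would drop the later hemorrhage or leak. The backstop sentence covers only serious events thought possibly related, does not mention withdrawn patients, and itself contradicts a rule of no further collection. Wording in an attachment would not remove the conflict between two sections of the protocol body.

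**Conclusion.** The concern holds. Section 4.4.2 and sections 8.1, 8.2 and 8.2.1 give incompatible instructions for a patient who withdraws after surgery and before day 30, and the protocol body does not reconcile them. Following 4.4.2 would give a less complete safety record, including for two named safety endpoints.

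The number of events lost is probably small and cannot be estimated from the documents. Sample size is not affected, nor is the primary visual-field outcome for patients who withdraw after the video is recorded. The conclusion rests on the protocol text alone, with Attachments A to D unseen. The point should be corrected, but it does not threaten the trial's main comparison.

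**What to change.** Reconcile 4.4.2 with 8.1, 8.2, 8.2.1 and 9.1. One or two sentences in 4.4.2 would do it, for example:

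> After withdrawal from study participation, and where the patient permits, adverse events through day 30 after surgery, and serious events to their outcome, will continue to be recorded from the routine clinical chart and reported under section 8. Where authorization to use health information is revoked, section 9.1 applies.

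Check the consent form and HIPAA authorization, and align their wording if they do not already allow this. The cost is a short amendment, which goes to the EC/IRB as section 11 requires, and a little chart review for the patients concerned. No visits are added.

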5.1 Description

Propofol (Diprivan)

5.2 Treatment Regimen

Anesthesia Protocol

Preoperative medications may be given according to routine clinical care, which may include Midazolam 1-2 mg IV prior to being taken to the operating room. Standard ASA monitors will be placed. Induction of general anesthesia will follow the normal standard of care. Induction of anesthesia for both groups will include: Propofol 2 mg/kg, Lidocaine 0.5-1 mg/kg, Fentanyl 1-2 mcg/kg, with muscle relaxation with either Succinylcholine 1-2 mg/kg or Cisatracurium 0.15-0.2 mg/kg for intubation. Maintenance of anesthesia will consist of Cisatracurium 0.03- 0.04 mg/kg and the appropriate anesthetic per protocol described below.

CONFIDENTIAL

This material is the property of Ochsner Clinic Foundation. Do not disclose or use except as authorized in writing by the study sponsor

Patients in the inhaled anesthesia group will receive Sevoflurane in an end expiratory concentration of 1.4% to 3% corresponding to near minimum alveolar concentration (MAC) of ~0.5-1.5%. The carrier gas flow for both groups will consist of a combination of oxygen and air to a total flow rate of 2 l/m to maintain oxygenation per standard of care. Patients in the TIVA group will receive an infusion of Propofol in a dose of 100-200 mcg/kg/min for maintenance. IA group will adjust the Sevoflurane concentration and TIVA group will adjust the Propofol and Remifentanil dosing with the goal of maintaining mean arterial pressure 70 -80 mmHg.

Both groups will be allowed to utilize Phenylephrine, Ephedrine, Labetalol or Esmolol as needed to maintain target blood pressure. Patients will be reversed with Neostigmine and Glycopyrrolate at the conclusion of the case. Post-operative pain relief will include either Morphine or Dilaudid per standard of care. No Acetaminophen may be given for either group for pain control.

Surgical Protocol

All patients are placed in 30 degree Reverse Trendelenberg positioning. 10 minutes prior to start of surgery, patients are pretreated with 4% cocaine-soaked nasal pledgets and local injection of 1% xylocaine with 1:100,000 epinephrine into the submucosa at the anterior attachment of the middle turbinate and crista ethmoidalis. Topical thrombin and epinephrine soaked pledgets will be available for intraoperative maintenance of hemostasis. Endoscopic sinus surgery will be completed following the modified Messerklinger technique, with utilization of endoscopic surgical equipment for video documentation of the surgical field. Recording equipment includes the Storz 4mm 0° rigid endoscope (Karl Storz, Tuttlingen, Germany) connected to a high definition camera and Olympus Evis Extra II light source. The video is recorded in MPEG2 digital format and transferred to the password protected study database. Visual field is recorded following the standardized method reported by Wormald et al., with the protocol as follows:

Prior to completion of surgery, old blood is suctioned from the nasal cavity with care not to traumatize mucosal surfaces and reinitiate bleeding. The surgical field is then recorded in a systematic fashion, with observation of four intranasal structures. Moving from anterior/superior to posterior/inferior, the frontal recess, ethmoidal cavity (endoscope positioned just anterior to the middle meatus), sphenoidal recess, and postnasal space are serially recorded for ten seconds each.

Following completion of surgery total blood loss will be calculated by the nursing circulator, with subtraction of the volume of intraoperative irrigation from the total volume contained in all suction canisters and saturated towels. The patient will be transferred to post-operative recovery and released home upon meeting established criteria. Patients will undergo routine postoperative follow-up, with evaluation at 1, 2, 4 weeks and as needed. A new SNOT-22 questionnaire will be completed as part of the postoperative week 2 and 4 visit.

CONFIDENTIAL

This material is the property of Ochsner Clinic Foundation. Do not disclose or use except as authorized in writing by the study sponsor

5.3 Method for Assigning Subjects to Treatment Groups

On the day of surgery, eligible participants will be admitted to the Day of Surgery Department, where a member of the Anesthesia team will review study information and confirm informed consent. A randomly assigned, sealed envelope will then be opened to assign participants to either the TIVA, or IA cohort. At no time will the patient or surgeon be made aware of the patient's cohort.

5.4 Preparation and Administration of Study Drug

Staff in the department of Anesthesia will administer perioperative medications in accordance with surgical standard of care.

5.5 Subject Compliance Monitoring

N/A as study intervention limited to perioperative maintenance of anesthesia.

5.6 Prior and Concomitant Therapy

Medications for induction, maintenance of anesthesia, reversal and postoperative recovery will be given as described in the “Anesthesia Protocol” (section 5.2).

5.7 Packaging

Packaging of study medication will be concealed from surgeons and study participants.

5.8 Blinding of Study Drug

At no time will the patient or surgeon be made aware of the patient's cohort. During the procedure the surgeon is blinded to the type of anesthesia by placement of a high drape at the head of the operative table. Study reviewers will be blinded to treatment arm without cohort assignment at time of review for determination of visual field score.

5.9 Receiving, Storage, Dispensing and Return

5.9.1 Receipt of Drug Supplies

Upon receipt of the of the study treatment supplies, an inventory must be performed and a drug receipt log filled out and signed by the person accepting the shipment. It is important that the designated study staff counts and verifies that the shipment contains all the items noted in the shipment inventory. Any damaged or unusable study drug in a given shipment (active drug or comparator) will be documented in the study files. The investigator must notify study sponsor of any damaged or unusable study treatments that were supplied to the investigator's site.

5.9.2 Storage

The study medication will be stored in the hospital pharmacy and distributed to Anesthesia personnel in accordance with surgical standard of care.

CONFIDENTIAL

This material is the property of Ochsner Clinic Foundation. Do not disclose or use except as authorized in writing by the study sponsor

5.9.3 Dispensing of Study Drug

Staff anesthesiologists will dispense study drug in the perioperative setting. Drug administration will be recorded and maintained in the surgical record.

6 Study Procedures

Participants make no clinic/hospital visits for purposes of study completion as all patient interaction limited to visits and surveys completed as part of routine clinical care.

6.1 Visit 1

Clinic presentation: A 22-item Sinonasal Outcome Test (SNOT-22) survey is completed per routine clinical care. Patients considering endoscopic sinus surgery for treatment of inflammatory paranasal sinus disease are initially screened for study participation. The principal investigator ([name]) presents the research purpose, personnel, procedures, risks and benefits of the study, and provides a written copy of the study consent for home review.

6.2 Visit 2

Preoperative visit: Study consent reviewed with an investigator and signed at this time. Enrolled patients will be assigned a randomly generated unique study identification number. The patient's demographic information will then be entered into the password-protected study database (Excel, Microsoft, Redwood, WA), which will be maintained on a HIPAA compliant server with access restricted to identified study computer maintained in the department of Otolaryngology.

6.3 Visit 3

Day of Surgery: Study consent reviewed and treatment group assigned. Intervention limited to perioperative maintenance of anesthesia with recording of deidentified endonasal endoscopic video for independent analysis of surgical visual field.

6.4 Visit 4

Routine 1-week postoperative follow-up.

6.5 Visit 5

Routine follow-up 4 weeks after date of surgery with completion of SNOT-22 survey.

6.6 Visit 5

Routine follow-up 12 weeks after date of surgery with completion of SNOT-22 survey.

CONFIDENTIAL

This material is the property of Ochsner Clinic Foundation. Do not disclose or use except as authorized in writing by the study sponsor

7 Statistical Plan

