Statistical Methodology	All parametric data is tested for normal distribution and characterized by mean +/- standard deviation. Differences between the visual field and change in quality-of-life measure for the two treatment groups are evaluated using a t -test. The association between the treatment groups and surgical procedure is tested using the chi-square test. The association between the treatment groups and pathological groups is tested using Fisher's exact test.
-------------------------	--

CONFIDENTIAL

This material is the property of Ochsner Clinic Foundation. Do not disclose or use except as authorized in writing by the study sponsor

1 Introduction

This document is a protocol for a human research study. This study is to be conducted according to US and international standards of Good Clinical Practice (FDA Title 21 part 312 and International Conference on Harmonization guidelines), applicable government regulations and Institutional research policies and procedures.

1.1 *Background*

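### The baseline for SNOT-22 change is not defined, and the only scheduled preoperative score is at Visit 1, at no fixed interval from surgery: a possible loss of precision, not a bias

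*Combined protocol and SAP*

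**What the plan says.** Section 6.1 (Visit 1) states: "Clinic presentation: A 22-item Sinonasal Outcome Test (SNOT-22) survey is completed per routine clinical care". Of the same visit it says: "Patients considering endoscopic sinus surgery for treatment of inflammatory paranasal sinus disease are initially screened for study participation".

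Section 6.2 (Visit 2) opens "Preoperative visit: Study consent reviewed with an investigator and signed at this time" and goes on to the study number and demographic data; it lists no SNOT-22. Section 6.3 (Visit 3) opens "Day of Surgery: Study consent reviewed and treatment group assigned" and adds the anesthetic intervention and the video; again no SNOT-22 is listed. Section 5.3 confirms that the allocation envelope is opened on the day of surgery.

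After surgery, section 6.6 has "Routine follow-up 12 weeks after date of surgery with completion of SNOT-22 survey", and section 6.5 has the same at 4 weeks. The surgical protocol in section 5.2 instead puts the postoperative SNOT-22 at weeks 2 and 4.

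Change in sinus-related quality of life is a secondary outcome (section 3.3). The Statistical Methodology entry of the Study Summary says "Differences between the visual field and change in quality-of-life measure for the two treatment groups are evaluated" by t-test, with no mention of baseline adjustment. No section says which score is the baseline, and none limits the time between Visit 1 and surgery.

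**The concern.** A change score needs a defined starting point. The only candidate that the text schedules is a routine-care form, completed at an unstated time before surgery. Whatever happens to symptoms between that form and the operation enters the patient's change score, although it has nothing to do with the anesthetic.

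Two things are at stake. The first is precision: a baseline further from surgery will usually correlate less with the postoperative score, and an unadjusted comparison of change carries that extra noise in full. The second is description: the mean change reported within each arm would combine movement before surgery with the response after it. A preoperative visit already exists at which a later score could be taken, and a score near surgery cannot be recovered once the patient has been operated on.

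**Working it through.** **Plan's own figure.** The plan gives no figure for SNOT-22. The sample size in section 7.1 (52 per arm, 2 × 52 = 104, raised to 110) was set from the visual-field scale and does not depend on this endpoint. It is used below only as the number per arm.

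**Step 1: does movement before surgery bias the arm comparison?** Assignment follows Visit 1, so any movement before the envelope is opened has the same distribution in both arms. A simulation of 20,000 trials checked this, with 52 per arm and an assumed correlation of 0.5 between a near-surgery baseline and follow-up. Drift is in SNOT-22 SD units.

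| Mean drift (SD of drift) | Mean within-arm change | Mean between-arm difference | Type I error |
|---|---|---|---|
| +0.3 (0.5) | 0.301 | −0.0004 | 4.8% |
| −0.5 (0.75) | −0.500 | −0.0005 | 4.85% |

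The drift passes in full into the within-arm change, with whichever sign it has. The arm comparison is unaffected on average.

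**Step 2: cost in precision if the correlation falls.** Assume equal SDs before and after surgery, and let r be the correlation between baseline and follow-up. The documents give no r; 0.7, 0.6 and 0.5 are assumptions.

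- Change score: variance = 2 × SD² × (1 − r). In units of SD² this is 0.60 at r = 0.7, 0.80 at 0.6 and 1.00 at 0.5.
- Ratios to r = 0.7: 0.80/0.60 = 1.33 and 1.00/0.60 = 1.67. Square roots: 1.15 and 1.29. The confidence interval widens by about 15% or 29%.
- ANCOVA: residual variance = SD² × (1 − r²), giving 0.51, 0.64 and 0.75.
- Ratios: 0.64/0.51 = 1.25 and 0.75/0.51 = 1.47. Square roots: 1.12 and 1.21. The interval widens by about 12% or 21%.

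If Visit 1 falls close to surgery, r hardly changes and the loss is near zero.

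**Step 3: a second model, with drift added to the early score.** Let ρ be the correlation of a near-surgery baseline with follow-up, and τ the SD of drift in SNOT-22 SD units. Both are assumed.

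- Change-score SD = √(2(1 − ρ) + τ²).
- ANCOVA residual SD = √(1 − ρ²/(1 + τ²)).

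Take an effect that has 80% power on the change score with a near-surgery baseline, at 52 per arm and two-sided 5%. At ρ = 0.5:

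| τ | Change-score SD | Power, t-test on change | Power, ANCOVA on the early score |
|---|---|---|---|
| 0 | 1.000 | 80% | 90% |
| 0.25 | 1.031 | 78% | 89% |
| 0.5 | 1.118 | 71% | 88% |
| 0.75 | 1.250 | 61% | 86% |

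Over ρ from 0.3 to 0.7 and τ from 0.25 to 0.75, the change-score SD rises by 2% to 39% and the power of the t-test lies between 78% and 52%. ANCOVA on the early score gives 93% to 75% over the same range.

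**The case against.** Five points can be made on the other side.

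1. *Timing of the surgical decision.* A reader might infer that Visit 1 precedes the decision to operate. The documents do not say so. Section 6.1 says only that patients are considering surgery, and section 4.3 places what appears to be the same screening encounter "during their preoperative visit in the Department of Otolaryngology". That wording leaves open that the Visit 1 form is completed close to surgery. The objection stands. The two sections also do not agree on where screening takes place, which is itself a reason to define the baseline.

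2. *Whether it is the only preoperative score.* Attachment C (the table of collected data) is listed but is not in the available text, and routine care may include a later form. The statement holds for the visible text alone.

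3. *Direction.* A reader might infer that an early baseline inflates the improvement within each arm. No section describes treatment or a long delay between Visit 1 and surgery, and eligibility (4.1, 4.2) sets no SNOT-22 threshold, so the design does not itself select high scores. Worsening before surgery would shrink the apparent improvement. Only a shift of unknown sign can be claimed.

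4. *Much of the loss comes from the analysis.* ANCOVA on a Visit 1 score has variance 0.64 at r = 0.6 and 0.75 at r = 0.5, against 0.60 for an unadjusted change from a near-surgery baseline at r = 0.7. The excess is then 7% and 25% in variance, or 3% and 12% in interval width, with no new data. This stands, and adjustment belongs in the fix. It does not make timing irrelevant, because a near-surgery baseline is also better under ANCOVA.

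5. *Visit 2 has no stated interval to surgery either, and the plan confines itself to routine surveys* (section 6: "Participants make no clinic/hospital visits for purposes of study completion"). Both are true. Visit 2 is still nearer to randomisation than Visit 1, day-of-surgery admission is another option, and neither needs an extra visit.

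**Conclusion.** The point holds as a minor gap in definition and precision. In the visible text the baseline for SNOT-22 change is not named, and the one scheduled candidate has no fixed relation to surgery. A reader might take this as a bias in TIVA versus IA; day-of-surgery assignment rules that out, and the simulation agrees.

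What remains is possible extra noise in one secondary endpoint and a within-arm change that is hard to interpret. The widening figures rest entirely on assumed correlations, and the drift-model power figures on assumed correlations and drift. The range includes almost no loss. The primary endpoint and the sample size are untouched. The change is worth making because it is cheap and has to be made before patients are operated on.

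**What to change.** - Collect SNOT-22 after consent is signed and before the envelope is opened, either at Visit 2 (6.2) or at day-of-surgery admission (6.3, 5.3).
- State that this score is the baseline for change in quality of life, and that the Visit 1 score is used only when it is missing.
- Record the number of days from the baseline score to surgery.
- In the Statistical Methodology entry, replace the unadjusted t-test on SNOT-22 change with an ANCOVA that adjusts for baseline.
- Reconcile the postoperative SNOT-22 times (weeks 2 and 4 in section 5.2; weeks 4 and 12 in sections 6.5 and 6.6), since that conflict leaves the other end of the change score undefined.

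Cost: one repeat of a 22-item form at an existing visit, a few minutes of patient time, and a few sentences in the protocol. The repeat form may fall outside routine care, so the opening statement of section 6 that surveys are routine only would need a small edit.
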